**PARTNERS HUMAN RESEARCH COMMITTEE
DETAILED PROTOCOL**

PRINCIPAL/OVERALL INVESTIGATOR

[name].

PROTOCOL TITLE

A Randomized Controlled Trial of an Advanced Care Planning Video Decision Support Tool for Patients with End-Stage Liver Disease (Clinicaltrials.gov Identifier NCT03557086)

FUNDING

NIH-NIDDK National Institute of Diabetes and Digestive and Kidney Diseases
4K24DK078772-10

VERSION DATE

Version 9: February 6, 2020

A Randomized Controlled Trial of an Advanced Care Planning Video Decision Support Tool for Patients with End-Stage Liver Disease

Version 9: February 6, 2020

SPECIFIC AIMS

The goal of this pilot randomized trial is to assess the feasibility and preliminary efficacy of an advanced care planning (ACP) video decision support tool for improving patients' knowledge regarding their goals of care options and end of life (EOL) decision-making in patients with end-stage liver disease (ESLD).

Aim 1: To assess the feasibility and acceptability of an ACP video decision support tool for patients with ESLD

- *Hypothesis 1: The intervention will be deemed feasible and acceptable if at least 60% of eligible patients are enrolled in the study and if at least 60% of patients randomly assigned to the video intervention report that the video is acceptable*

Aim 2: To assess the impact of an ACP video decision support tool on patients' knowledge about their EOL care options

- *Hypothesis 2: Patients randomly assigned to the video intervention will report improved knowledge of their EOL care options compared to those randomized to the verbal narrative control*

Aim 3: To assess the impact of an ACP video decision support tool on patients' preferences for EOL care

- *Hypothesis 3: Patients randomly assigned to the ACP video will be more likely to prefer comfort care compared to those randomized to the verbal narrative control arm*
- *Hypothesis 4: Patients randomly assigned to the video intervention will be more likely to forgo cardiopulmonary resuscitation (CPR) and intubation compared to those randomized to the verbal narrative control arm*

Aim 4: To assess the impact of an ACP video decision support tool on patients' documented EOL care preferences

- *Hypothesis 5: Patients randomly assigned to the video intervention will be more likely to have their code status documented in the electronic healthcare record compared to those randomized to the verbal narrative control arm*

BACKGROUND AND SIGNIFICANCE

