of the study: to better understand how much patients with ESLD know about ACP and EOL care preferences. The RA will also explain that the study requires completing a 15-minute baseline questionnaire asking participants about their CPR and intubation preferences, eliciting prior advance care planning discussions, and assessing their knowledge regarding CPR and intubation. The RA will undergo standardized training in all aspects of the research protocol, including the use of structured scripts to administer the questionnaires (**Appendix A**). For patients agreeing to participate in the study, the RA will obtain written informed consent from the participants and provide them with a copy of the signed consent form.

After obtaining informed consent, the RA will administer the Short Portal Mental Status Questionnaire (**Appendix B**) to participants to confirm final eligibility. Immediately following enrollment, the RA will administer a 15-minute baseline questionnaire (see “Study Measures” below) that will include the following: demographics, self-reported health status, baseline EOL care preferences, CPR and intubation preferences, and a questionnaire assessing patients’ knowledge of EOL care options.

Randomization

After enrollment and completion of the baseline questionnaires, participants will be randomized in 1:1 fashion without any stratification to either the control group (verbal narrative alone) or the intervention group (video decision support tool) using a random computer generated list, with assignments concealed in numbered envelopes.

The Intervention Arm

Our group, the VIDEO Consortium (Video Images of Disease for Ethical Outcomes), has developed several video decision support tools to assist patients with advance care planning.^{38,39,44} We have previously developed a five-minute advance care planning video for patients with advanced cancer⁴⁵, which has been adapted for this study.

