Immediately after completing the baseline assessment and randomization, patients assigned to the video intervention arm will view the 3-minute advance care planning video for patients with ESLD on an iPad in the presence of the RA. We will use standardized procedures to minimize the interaction between the RA and patient while the patient is viewing the video. The RA will not be permitted to comment or answer questions while the patient views the video. Patients will be instructed to watch the video once without any interruption and will have no further exposure to the video. If patients have questions about the video or their EOL care options, the RA will instruct them to discuss their questions with their medical team.

The finalized video can be viewed by the IRB at the following link:

<https://vimeo.com/269740750>

Access Code: mghirb

The Control Arm

Immediately after completing the baseline assessment and randomization, patients assigned to the verbal narrative control arm will listen to the same description of the 3 goals of care used in the video arm read out loud by the RA (**Appendix C**). We will use standardized procedures to minimize interaction between the RA and patients during the interview. Specifically, the RA will not be permitted to comment or answer questions while the patients listen to the verbal narrative. Patients will be instructed to ask their physicians any questions they may have about goals of care.

Study Measures

A Randomized Controlled Trial of an Advanced Care Planning Video Decision Support Tool for Patients with End-Stage Liver Disease

Version 9: February 6, 2020

We will administer the following study measures at baseline prior to randomization, and immediately after the video or verbal narrative in the intervention and control group, respectively according to the timeline displayed in **Table 1**:

- *Demographics*: Patients will complete a demographic questionnaire at baseline detailing their age, sex, race/ethnicity, religion, relationship status, educational level, living situation, employment status, and self-reported health status (“Relatively healthy”, “Relatively healthy and terminally ill”, “Seriously ill and not terminally ill”, “Seriously ill and terminally ill”)⁴⁶ (**Appendix D**)
- *EOL Care Preferences*: Patients will report their EOL care preferences as follows: life-prolonging care, limited medical care, comfort care, or unsure. (**Appendix E**)

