We will collect and enter all patient data electronically using Research Electronic Data Capture (REDCap). The REDCap Survey is a tool for building and managing online surveys. Vanderbilt University, in collaboration with a consortium of institutional partners, has developed this software and workflow methodology for electronic collection and management of research and clinical trial data. Our research team has extensive experience using REDCap and will create and design the surveys in a web browser, with institutional information technology support. The REDCap Survey system offers secure, HIPAA compliant, web-based applications that provide an intuitive interface for participants to enter data, with real-time validation rules at the time of entry.

Participants will use tablet computers to complete questionnaires in clinic. If any participants refuse or are unable to complete the questionnaires on the computer, they will be permitted to use hard-copy paper versions. In addition, the patient data collected from the electronic health record will be abstracted throughout the study and directly inputted into REDCap.

Study Outcomes

- **Primary Outcome:** The primary outcome is feasibility. The proposed video intervention will be deemed feasible if at least 60% of eligible patients are enrolled in the study. The 60% feasibility cut-off is commonly used in behavioral intervention studies.⁵¹⁻⁵³
- **Secondary Outcomes:** The secondary outcomes will include patients' comfort/satisfaction with the video, patients' stated post-intervention EOL care preferences categorized as four options: Life-prolonging care, limited medical care, comfort care, or unsure; individual preferences for CPR and intubation before and after intervention in the verbal narrative and video groups; and change in knowledge scores after receiving the verbal narrative or video

Sample Size Calculation

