We will randomize up to 70 patients with ESLD for this project. The primary endpoint of the study is feasibility. We chose the sample size of 70 patients based on the feasibility of completing the project during the proposed timeframe and the ability to assess the preliminary efficacy of the intervention. Consistent with the behavioral intervention literature, at least 20 patients are needed in each group in a pilot study to estimate a parameter.^{54,55} Therefore, the proposed sample size will provide us with preliminary data that can be utilized to determine the effect size and adequately power future randomized trials. This is a commonly utilized study design for pilot testing of behavioral interventions and is consistent with the National Institute of Health Stage Model for Intervention Development. While the feasibility of the intervention can be assessed using a single-arm design, preliminary efficacy is better assessed utilizing a control group as we are proposing in this trial.

A Randomized Controlled Trial of an Advanced Care Planning Video Decision Support Tool for Patients with End-Stage Liver Disease

Analysis Plan

We will report baseline demographic and clinical characteristics of all study participants using means and proportions to describe continuous and categorical variables, respectively. Because this is a pilot study, we will use conservative ($\alpha = 0.05$) and liberal ($\alpha = 0.20$) critical values to assess statistical significance between the two arms in this pilot study.

Aim 1: The primary endpoint of the proposed study is feasibility. The proposed video intervention will be deemed feasible if at least 60% (95% CI +/- 13.6%) of eligible patients are enrolled in the study and complete at least 60% of the intervention sessions. The proposed video intervention will be deemed acceptable if at least 75% of patients randomized to the intervention arm report satisfaction and comfort with the video.

Aim 2: Changes in knowledge scores from before and after the intervention will be compared between the two groups using two-sample t-tests.

Aim 3: Post-intervention EOL care preferences (life-prolonging care, limited medical care, and comfort care), CPR preferences, and intubation preferences will be compared between the two groups using Fisher's exact tests. The change in CPR and intubation preferences before and after the intervention within each group will be compared using McNemar tests.

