Appendix G: Impression and acceptability of the video (intervention arm only)

1) Was the video helpful in improving your understanding about your choices for medical care?

- 0 Very helpful
- 1 Somewhat helpful
- 2 A little helpful
- 3 Not helpful

2) Did you feel comfortable seeing the video in order to help you answer the questions regarding medical care?

- 0 Very comfortable
- 1 Somewhat comfortable
- 2 Not comfortable
- 3 Don't know

3) Would you recommend the video to other patients with advanced liver disease who are facing a similar decision?

- 0 I would definitely recommend it.
- 1 I would probably recommend it.
- 2 I would probably not recommend it.
- 3 I would definitely not recommend it.

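### Aim 1 has two acceptability thresholds (60% and 75%) with no rule saying which governs, and the Analysis Plan adds a session-completion clause to the primary feasibility rule that the other two statements of it lack

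*Combined protocol and SAP*

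**What the plan says.** **Acceptability.** Hypothesis 1 (Specific Aims) counts the video as acceptable if "at least 60% of patients randomly assigned to the video intervention report that the video is acceptable". The Analysis Plan, Aim 1, says it will be "deemed acceptable if at least 75% of patients randomized to the intervention arm report satisfaction and comfort with the video". Study Outcomes lists comfort/satisfaction with the video as a secondary outcome and gives no threshold.

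**Measurement.** Study Measures names the measure as acceptability of the video and assigns it three items, given to the video arm only. Table 1 (Data Collection Timeline) lists the video-arm measure as comfort/satisfaction. The items are in Appendix G. Item 1 asks "Was the video helpful in improving your understanding about your choices for medical care", item 2 asks about comfort in seeing the video, and item 3 asks about recommending it. Each has four answer options, and item 2 includes a 'Don't know' option.

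**Feasibility (primary outcome).** Study Outcomes states: "The proposed video intervention will be deemed feasible if at least 60% of eligible patients are enrolled in the study". Hypothesis 1 has the same enrolment condition and nothing more. The Analysis Plan, Aim 1, requires that at least 60% "of eligible patients are enrolled in the study and complete at least 60% of the intervention sessions". The Intervention Arm section describes one exposure: "Patients will be instructed to watch the video once without any interruption and will have no further exposure to the video".

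**The concern.** Both acceptability statements define when the same video, in the same arm and under the same aim, earns the same verdict, yet the bars are 15 percentage points apart. Nothing in the document ranks one above the other. A result from 60% to just below 75% could be reported either way, and the choice could be made after the data are seen. The undefined numerator adds to this freedom. On four-option items, whether a 'somewhat' answer counts as positive, and whether one item or all three must be positive, can move the observed share as much as the threshold does.

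The session clause touches the primary outcome. It appears in one of three statements of the rule. It speaks of sessions where each video patient has one viewing, and it does not say whether completion is counted among video patients, all enrolled patients or all eligible patients. How demanding the condition is depends on that choice.

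**Working it through.** **Plan's own figure.** The two thresholds are chosen criteria, so there is nothing to reproduce. The only calculated figure in the Aim 1 rule is the half-width of 13.6 points attached to 60% enrolment. From 1.96 × √(0.6 × 0.4 / n), n = 50 gives 13.6 points and n = 70 gives 11.5. That is a separate matter, and nothing below uses it.

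**Inputs.** Up to 70 patients are randomised (Sample Size Calculation), and "participants will be randomized in 1:1 fashion without any stratification" (Randomization). That gives 70 / 2 = 35 video patients at full size. This is an assumption, because 70 is a maximum. True acceptability and completion rates are not given, so a range is shown.

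**Step 1: passing counts.** With the same response scored under both rules:
- 60% rule: 0.60 × 35 = 21, so 21 or more pass.
- 75% rule: 0.75 × 35 = 26.25, so 27 or more pass.
- 21 to 26 of 35 (60.0% to 74.3%) is acceptable under Hypothesis 1 and not acceptable under the Analysis Plan.

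**Step 2: chance of opposite verdicts.** P(21 ≤ X ≤ 26) = P(X ≥ 21) − P(X ≥ 27), with X ~ Binomial(35, p):

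| Assumed true rate p | P(X ≥ 21) | P(X ≥ 27) | Opposite verdicts |
|---|---|---|---|
| 60% | 0.573 | 0.026 | 55% |
| 65% | 0.789 | 0.089 | 70% |
| 70% | 0.927 | 0.234 | 69% |
| 75% | 0.984 | 0.474 | 51% |
| 80% | 0.998 | 0.745 | 25% |
| 85% | 1.000 | 0.931 | 7% |
| 90% | 1.000 | 0.994 | 1% |

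With 20 video patients, the pilot minimum per group that the plan cites, the passing counts are 12 and 15. The conflict range is 12 to 14, and the chances at the same rates are 47%, 52%, 47%, 34%, 19%, 7% and 1%.

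**Step 3: session clause, two readings.**
- *Completion among patients assigned to video.* At least 0.60 × 35 = 21 must finish. The chance of failing is P(X ≤ 20) with X ~ Binomial(35, c). At assumed completion c = 80% it is 0.0018, or 0.2%. At 70% it is 0.073, and at 90% it is negligible.
- *60% of eligible patients both enrol and complete, both arms counted.* Required completion is 0.60 / enrolment. At 65% enrolment this is 0.60 / 0.65 = 92%. At 70% it is 0.60 / 0.70 = 86%.

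**The case against.** The strongest reply is one of proportion. Acceptability is a secondary outcome of a pilot meant to supply preliminary data, and if nearly everyone likes the video both rules pass. That stands in part: the chance of opposite verdicts is 7% at a true rate of 85% and 1% at 90%. But the plan states no expected rate, and feasibility and acceptability are Aim 1 of this pilot, so their decision rules should not conflict.

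The session clause also matters less in practice than its wording suggests. The video lasts 3 minutes and is shown straight after randomisation with the research assistant present, so even 86% or 92% completion is plausible.

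Three stronger readings are tempting, and the documents do not support them.
- *That acceptability has no instrument because no item asks about satisfaction.* Study Measures, Table 1 and Study Outcomes together treat acceptability and comfort/satisfaction as one outcome measured by Appendix G. Only the cut-off and the combination rule are missing.
- *That the two rules score different responses, so the clash persists even when acceptability is high.* This needs an assumed gap between two response definitions. The documents give no such gap and point to one outcome.
- *That the feasibility rule cannot be met, because 1:1 allocation leaves half of enrolled patients with no video.* This would require control patients to count as failures for a video they were never offered. No passage says so. It shows loose wording, not a likely result.

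**Conclusion.** The concern holds as two inconsistencies in current text. First, the acceptability verdict has two thresholds, no statement of which governs, and no defined responder. With an assumed 35 video patients and one response scored under both rules, 21 to 26 positive answers reverse the verdict. The chance of landing there is at least 51% for assumed true rates of 60% to 75%, falls to 25% at 80%, and is small from 85% upwards. Second, the primary feasibility rule carries an extra condition in the Analysis Plan only. Read as completion among video patients, it has almost no effect if completion is 80% or more. Read across all eligible patients with both arms counted, it demands 86% to 92% completion at 70% to 65% enrolment. The documents do not show which threshold or which feasibility wording was intended. This should be fixed, but it does not undermine the design.

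**What to change.** Before the data are examined:

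1. State one acceptability threshold in both Hypothesis 1 and the Analysis Plan, with all patients randomised to video as the denominator. The sponsor chooses it. Keeping 75% avoids lowering the bar in the Analysis Plan. If 60% is chosen, the plan should say that the bar was lowered.
2. Define a responder on the Appendix G items: which item or composite is used and which answer options are positive. Count 'Don't know' on item 2 and missing answers as not positive.
3. Make the feasibility rule identical in Hypothesis 1, Study Outcomes and the Analysis Plan. Either drop the session clause and report descriptively the share of video-arm patients who finish the video, or state the clause in all three places with the video arm as its denominator.

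The cost is wording only, with no new data. One of the two stated acceptability bars changes, and dropping the clause removes a condition that the Analysis Plan now places on the primary outcome.

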- *CPR Preferences*: Patients will report their CPR preferences as follows: “Yes, attempt CPR”, “No, do not attempt CPR”, or “Not sure.” (**Appendix E**)
- *Intubation Preferences*: Patients will report their intubation preferences as follows: “Yes, attempt intubation”, “No, do not attempt intubation”, or “Not sure.” (**Appendix E**)
- *Knowledge Questionnaire*: We will assess patients’ knowledge of goals of care as in previous studies using 5 true/false questions and 1 multiple choice question, each worth 1 point, for a summary score of 0 to 6 (higher score reflects greater knowledge)^{45,47,48} (**Appendix F**)
- *Acceptability of the Video*: For the video intervention arm alone, we will administer 3-items assessing patients’ comfort with watching the video, whether they find the video helpful in their understanding of the EOL care options, and whether they would recommend it to others.⁴⁹ (**Appendix G**)

We will also obtain the following important covariates and outcomes:

- *Disease-related variables*: We will collect variables from the EHR at the time of enrollment, including the etiology of ESLD, presence of clinically-evident decompensating events (ascites, esophageal variceal bleed, hepatic encephalopathy, or multiple), Model of End-Stage Liver Disease Sodium (MELD-Na) score, reason for transplant ineligibility, and clinical comorbidities using the modified Charlson Comorbidity Index.⁵⁰
- *Code Status Documentation in the EMR*: The RA will review the EHR to collect whether clinicians’ documented patients’ code status in the EMR (yes: documented, no: not documented) 3 months after study enrollment.

Table 1: Data Collection Timeline

	Baseline	Post-intervention	3 months post-enrollment
Demographics	X		
Self-Reported Health Status	X		
EOL Care Preferences	X	X	
CPR Preferences	X	X	
Intubation Preferences	X	X	

Knowledge Questionnaire	X	X	
Comfort/Satisfaction with Video (Intervention group only)		X	
Disease-related variables	X		
Code status documentation			X

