APPENDIX A: Script for Administering the Educational Methods

Introduction

Research staff member: My name is (state name) and I am a working on a project about what people prefer when receiving medical care at the end of life. The goal of this project is to understand what people think and what they like better when getting medical care for advanced liver disease. You are being asked to take part in this study because you have advanced liver disease. Taking part in the project is strictly up to you. You can decide to not answer any of the questions if you wish, and can stop the interview at any time. You may also see an educational video during this survey, and you can stop the video at any time. Taking part in this project will have no bearing on your current care. This interview will last about a half hour. Does this sound like a project you would like to participate in?

If YES: Research staff member will obtain written consent and administer the Short Portable Mental Status Questionnaire

If NO: Research staff member thank the patient and end the interview

Screening: Short Portable Mental Status Questionnaire (Appendix B)

Research staff member: First, I will ask you some general questions.

Administer Appendix B

If score is ≤ 6 : Research staff member thank the patient and end the interview

If score is 7 or higher: Research staff member will continue to baseline questionnaires

Baseline Questionnaires (Appendices D, E, and F)

Here are some questionnaires to fill out on your own, which will help us to learn more about how people with advanced liver disease feel and what they like better when getting medical treatment. Please ask the interviewer if you need help at any time

Study Randomization - If randomized to VIDEO

Research staff member: I will now play an educational video tool about the different medical care options for patients with advanced liver disease. I will not be able to answer any questions about the content of the video. However, you should feel free to bring up any questions that you have about choices for medical care for patients with advanced liver disease to your care team. Do you have any questions about the study procedures before we begin?

If YES: Research staff member will address questions

If NO: Research staff member will play the educational video tool

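### Aim 2 analyses knowledge by a t-test on change scores; regression on arm and baseline score estimates the same difference, usually more precisely, for one degree of freedom

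*Combined protocol and SAP*

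**What the plan says.** The Analysis Plan gives Aim 2 one sentence: "Changes in knowledge scores from before and after the intervention will be compared between the two groups using two-sample t-tests". Study Outcomes lists the matching secondary outcome as "change in knowledge scores after receiving the verbal narrative or video".

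The data for a baseline-adjusted analysis are already collected. Study Measures says: "We will administer the following study measures at baseline prior to randomization, and immediately after the video or verbal narrative". Table 1 (Data Collection Timeline) marks the Knowledge Questionnaire at both baseline and post-intervention. The instrument has six one-point items, scored 0 to 6. Under Randomization: "After enrollment and completion of the baseline questionnaires, participants will be randomized in 1:1 fashion without any stratification".

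No aim in the Analysis Plan has a model with a covariate. The Sample Size Calculation gives no power, SD or detectable difference for Aim 2, but says the trial will provide "preliminary data that can be utilized to determine the effect size and adequately power future randomized trials".

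**The concern.** A change score does use baseline, but it subtracts the whole baseline score from every patient's post score, whatever the data show about how strongly the two are related. If the true within-arm slope is below 1, this over-corrects and adds baseline noise to the comparison. Regression on arm and baseline estimates the slope instead. Because baseline precedes randomisation, both methods target the same quantity, so the choice between them is one of precision.

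Knowledge is a secondary outcome of a pilot whose primary endpoint is feasibility, and that conclusion does not depend on this choice. But Aim 2 is a stated efficacy aim, and its estimate is meant to inform later trials. With at most 70 patients, avoidable imprecision in that estimate is worth removing when the remedy is nearly free.

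**Working it through.** **Inputs from the documents.** Up to 70 patients, 1:1, so n = 35 per arm and N = 70. Critical values are 0.05 and 0.20. Sidedness is not stated, so two-sided is assumed. The post score is taken in the same session, and no loss is assumed.

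**Inputs not in the documents.** The baseline–post correlation ρ, the SD ratio k (post SD / baseline SD) and the effect size are not given. All are assumptions below. There is no Aim 2 figure in the plan to reproduce.

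**Step 1: same target, ordered variances.** Randomisation makes the expected baseline difference zero. So (post difference − b × baseline difference) has the same expectation for any fixed b. The change score sets b = 1. With 1:1 allocation the pooled within-arm slope is the b that minimises the large-sample variance, whether or not the relation is linear. With baseline SD σx and post SD σy, the per-patient variances are:

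- change: σx² + σy² − 2ρσxσy
- regression: σy²(1 − ρ²)
- gap (change − regression): (σx − ρσy)², which is never negative and is zero only when the slope ρσy/σx equals 1.

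**Step 2: cost of estimating the slope.** The expected inflation is 1 + 1/(N − 4). That is 1 + 1/66 = 1.0152 at N = 70 and 1 + 1/36 = 1.0278 at 20 per arm. Residual degrees of freedom fall from 68 to 67.

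**Step 3: equal SDs.** In SD units, Var(change) = 2(1 − ρ) × 2/35 and Var(regression) = (1 − ρ²) × 1.0152 × 2/35. The ratio is (1 + ρ)/2 × 1.0152. At ρ = 0.5 this is 0.75 × 1.0152 = 0.761. Power is noncentral t for an assumed true difference of 0.5 SD. Percentages come from unrounded values.

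| ρ | Variance ratio | 95% CI half-width, change vs regression | CI narrower by | Power, α 0.05 | Power, α 0.20 |
|---|---|---|---|---|---|
| 0.3 | 0.660 | 0.564 vs 0.459 | 19% | 41% vs 57% | 68% vs 81% |
| 0.5 | 0.761 | 0.477 vs 0.416 | 13% | 54% vs 66% | 79% vs 87% |
| 0.7 | 0.863 | 0.369 vs 0.343 | 7% | 76% vs 82% | 92% vs 95% |
| 0.8 | 0.914 | 0.302 vs 0.288 | 4% | 90% vs 93% | 98% vs 98% |
| 0.9 | 0.964 | 0.213 vs 0.210 | 2% | 99.6% vs 99.7% | 100% vs 100% |

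With equal SDs the break-even point solves (1 + ρ)/2 × 67/66 = 1, giving ρ = 65/67 = 0.97.

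**Step 4: unequal SDs.** The ratio is k²(1 − ρ²)/(1 + k² − 2ρk) × 1.0152.

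- k = 0.8, ρ = 0.5: 0.64 × 0.75/0.84 × 1.0152 = 0.580.
- k = 1.25, ρ = 0.8 (slope 1.25 × 0.8 = 1): 0.5625/0.5625 × 1.0152 = 1.015, a 1.5% loss.

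**Step 5: does a bounded, whole-number score change this?** Rounded 0 to 6 scores with a ceiling were simulated at 35 per arm, 20,000 runs per setting. All inputs were assumed: baseline mean 4, SD 1.3, gains of 0.4 and 1.1, and 12% of patients at 6 at baseline.

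- Both methods estimated the same difference, about 0.59 points.
- Variance ratios were 0.61, 0.69, 0.77, 0.80 and 0.83 at observed correlations of 0.32, 0.50, 0.69, 0.78 and 0.86.
- With no effect the ratios were 0.66 to 0.92. Type I error at 0.05 was 0.047–0.052 for the t-test and 0.049–0.051 for regression.

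A separate simulation with a lower assumed baseline mean (3.5) gave ratios of 0.57 to 0.81. Regression does not remove the ceiling, but the ceiling does not invalidate either analysis.

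**The case against.** The strongest reply is that nothing is wrong. The t-test is valid, the outcome is secondary, and no power claim for Aim 2 is undermined. All of that stands, and it is why this is a recommended improvement and not a required correction.

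The gain also rests on assumed correlations. The Appendix A script tells patients "This interview will last about a half hour", and both tests fall within that one interview, so ρ may be high. At 0.8 or 0.9 the benefit is small, and with a slope of 1 there is a slight loss. This stands as a limit on the size of the gain. Against it, a slope of 1 requires post SD = baseline SD/ρ, so post scores would have to be more spread out than baseline scores. The narrative in Appendix C directly covers points tested in Appendix F, such as the poor results of CPR and the freedom to change one's wishes. Gains towards a maximum of 6 would tend to compress the post scores and push the slope below 1. That is an inference, not a documented fact.

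Three further points are fair:

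- The change-score estimate is unbiased, and both scores are kept, so an adjusted estimate could be computed later. But choosing it after seeing the data is weaker than specifying it now.
- The plan promises tests and no confidence interval for Aim 2. The imprecision is still there in any effect estimate carried forward, whether or not an interval is printed.
- Study Outcomes words the endpoint as change. Regressing change on arm and baseline gives the identical arm coefficient and standard error, so that wording is no obstacle.

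**Conclusion.** The point holds as an efficiency improvement to a secondary aim. The planned test is valid. The baseline-adjusted regression estimates the same difference and in large samples is never less precise under 1:1 allocation. At N = 70 with equal SDs, the variance falls by 34% at ρ = 0.3 (1 − 0.660), 24% at 0.5 (1 − 0.761) and 4% at 0.9 (1 − 0.964). At ρ = 0.5, regression on 70 patients is worth a change-score analysis of about 92 (70/0.761). The downside is about 1.5% in variance when the slope is 1.

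These sizes rest on assumed correlations, SD ratios and, for power, an assumed 0.5 SD difference. The documents cannot narrow the range. The direction of the result does not depend on those assumptions, except when the slope is close to 1.

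**What to change.** Replace the Aim 2 sentence in the Analysis Plan with wording such as:

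> Post-intervention knowledge score will be compared between arms by linear regression on arm and baseline knowledge score, reporting the adjusted mean difference with 95% CI. Mean change will be described by arm, and the two-sample t-test on change will be a sensitivity analysis.

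To keep the Study Outcomes wording unchanged, use change as the dependent variable with the same two regressors; the arm estimate is identical. Also report the baseline and post SDs and their correlation, which a future sample size calculation needs.

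The cost is a short text change, a few extra reported quantities and one degree of freedom: about 1.5% in variance at N = 70, or 2.8% at 20 per arm. No new data are needed.
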